3.4 Investigational Plan

For this China-specific protocol, it is expected that at least 20 patients in each Cohort 1 and Cohort 2, and up to 25 patients in Cohort 3 with advanced solid tumors with evidence of a *RET* gene alteration in tumor and/or blood (e.g., gene rearrangement fusions and/or mutations, excluding synonymous, frameshift, or nonsense mutations) will be enrolled to one of three cohorts (Figure 3-1) as noted below to better characterize the safety and efficacy of selpercatinib in patients with specific abnormalities in *RET*. For Cohort 1 and 2, evidence of a *RET* gene alteration in tumor (i.e., not just blood) as defined in Table 3-1 is required (a positive germline test for a *RET* mutation is acceptable for patients with MTC).

Enrollment will be based on tumor type, type of *RET* alteration, and prior treatment:

- Cohort 1: Advanced *RET* fusion-positive solid tumor progressed on or intolerant to ≥ 1 prior standard therapy, or patients who declined or not suitable for standard first line therapy in the opinion of the Investigator (refer to Table 4-1 for standard therapies). For lung cancer, only patients harboring *RET-KIF5B*, *RET-CCDC6*, *RET-NCOA4* can be enrolled in Cohort 1. For other solid tumors, patients with any *RET* fusions can be enrolled in Cohort 1.
- Cohort 2: Advanced *RET*-mutant MTC with or without prior systematic therapy
- Cohort 3: Advanced *RET* altered solid tumor
 - Cohorts 1-2 without measurable disease;
 - Other *RET*-altered solid tumor or other *RET* alteration/activation not meeting the requirements for Cohorts 1 or 2;
 - MTC syndrome spectrum cancers (e.g. MTC, pheochromocytoma) with neuroendocrine features/differentiation or poorly differentiated thyroid cancers with other *RET* alteration/activation may be allowed with prior Sponsor approval;
 - Known cfDNA positive for a *RET* gene alteration and not able to be determined in tumor or FISH positive in tumor without PCR/NGS result may be allowed with prior Sponsor approval.

Selpercatinib will be administered in oral form at 160 mg BID. Each cycle will consist of 28 days.

Primary endpoint: ORR per RECIST 1.1 by independent review committee.

Secondary endpoint: ORR per RECIST 1.1 by investigator, DOR, CNS ORR, CNS DOR, CBR, TTR, TTBR, CBR, PFS, OS, PK, safety

Abbreviations: BID-twice daily, MTC-medullary thyroid cancer, DOR- duration of response, CNS ORR- central nervous system objective response rate, CNS DOR- central nervous system duration of response, CBR- clinical benefit rate, TTR- time to response, TTBR- time to best response, PFS-progression-free survival, OS- overall survival, PK- pharmacokinetic

Figure 3-1 Study Schema

3.5 Definition of *RET* Alterations

The specific *RET* gene alterations required for enrollment to Cohort 1 and 2 are defined in [Table 3-1](#). *RET* mutations and fusions will be identified from a laboratory with CNAS, EQA, CLIA, CAP or similar certification, so long as a written Molecular Pathology Report is available and clearly asserts the presence of the referenced *RET* alteration.

Table 3-1 Definition of *RET* Alterations

| |
|--|
| RET mutation* |
| Previously reported activating RET gene mutation excluding synonymous, frameshift, or nonsense mutations. Refer to Appendix B (Table 11-2) for examples. For MTC, RET gene mutation not known to be activating may be enrolled with Sponsor approval to Cohort 2. |
| RET fusion* |
| By PCR or NGS (FISH as the only molecular result is acceptable for Cohort 3, but not Cohort 1). |
| RET mutation* or RET fusion* |
| No other known validated driver alteration(s). Refer to Appendix C for examples. |
| * According to laboratory with CNAS, EQA, CLIA, CAP or similar certification, so long as a written Molecular Pathology Report is available and clearly asserts the presence of the referenced RET alteration. |

Abbreviations: CNAS-China National Accreditation Service for Conformity Assessment; EQA; CLIA-Clinical Laboratory Improvement Amendments; CAP-College Of American Pathologists; FISH-Fluorescence in Situ Hybridization; MTC-medullary thyroid cancer; NGS-next generation sequencing; PCR-polymerase chain reaction.

3.6 Number of Patients

Approximately 75 patients will be enrolled.

A statistical justification of sample/cohort size is provided in [Section 9.3](#).

3.7 Investigational Sites

Approximately 40 institutions will be recruited to enroll patients.

4 Selection of Study Population

Prospective approval of protocol deviations to recruitment and enrollment criteria, also known as protocol waivers or exemptions, is not permitted. Potential patients age 18 and older must sign an informed consent form before any study-specific screening tests may be conducted.

4.1 Inclusion Criteria

1. Patients with a locally advanced or metastatic solid tumor who:
 - have progressed on or are intolerant to standard therapy, or
 - no standard therapy exists, or in the opinion of the Investigator, are not candidates for or would be unlikely to tolerate or derive significant clinical benefit from standard therapy, or
 - decline standard therapy.
2. Prior MKIs with anti-RET activity are allowed. Refer to [Appendix A](#) for examples of MKIs with anti-RET activity. However, prior treatment with a selective RET inhibitor(s) (including investigational selective RET inhibitor(s), such as BLU-667, RXDX-105) is prohibited. The specific agent(s), duration of treatment, clinical benefit, and reason for discontinuation (e.g., PD, drug toxicity, or intolerance) should be documented for all kinase inhibitors the patient has been exposed to.
3. Evidence of a *RET* gene alteration in tumor and/or blood (e.g., gene rearrangement and/or mutation, excluding synonymous, frameshift, or nonsense mutations), as identified through molecular assays, as performed for clinical evaluation. The *RET* alteration result should be generated from a laboratory with certification by CNAS, EQA, CLIA, CAP or other similar certification. The Sponsor should be contacted to discuss test results from labs where such certification is not clearly demonstrated to determine eligibility.

Notes:

- A positive germline test for a *RET* mutation is acceptable for patients with MTC.
 - Local testing in a CNAS, EQA, CLIA, CAP or other similar certified laboratory is sufficient.
 - In all cases, a redacted/coded Molecular Pathology Report or other report(s) describing tumor and/or blood *RET* (and other) alternation analysis should be submitted to the Sponsor or designee during/prior to eligibility.
4. Measurable or non-measurable disease as determined by RECIST v1.1.
 5. At least 18 years of age.
 6. Eastern Cooperative Oncology Group (ECOG) performance status score of 0, 1, or 2, with no sudden deterioration 2 weeks prior to the first dose of study treatment.
 7. Life expectancy of at least 3 months.
 8. Archived tumor tissue sample available for Cohort 1 and 2.

Notes:

- Patients who do not have adequate archival tumor tissue available (refer to specific archival tissue requirements in Section 7.7.5.1) may undergo a fresh tumor biopsy, if it is considered safe to perform, prior to treatment.
 - If archived tumor tissue was obtained prior to progression on the last MKI with anti-RET activity, the patient should undergo a fresh tumor biopsy, if it is considered safe to perform, prior to treatment (optional).
9. Adequate hematologic status, defined as:
 - Absolute neutrophil count (ANC) $\geq 1.0 \times 10^9/L$ not requiring growth factor support for at least 7 days prior to treatment, and
 - Platelet count $\geq 75 \times 10^9/L$ not requiring transfusion support for at least 7 days prior to treatment, and
 - Hemoglobin (Hb) ≥ 9 g/dL not requiring transfusion support or erythropoietin for at least 7 days prior to treatment.
 10. Adequate hepatic function, defined as:
 - Alanine aminotransferase (ALT) or aspartate aminotransferase (AST) $\leq 2.5 \times$ the upper limit of normal (ULN) or $\leq 5 \times$ ULN with documented liver involvement (such as liver metastasis or a primary biliary tumor) and
 - Total bilirubin $\leq 1.5 \times$ ULN or $\leq 3 \times$ ULN with documented liver involvement (patients with Gilbert's Disease may be enrolled with prior Sponsor approval).
 11. Adequate renal function, with estimated glomerular filtration rate ≥ 30 mL/minute. Sites can use their own clinical standard for eGFR. If no clinical standard, below MDRD study equation can be used: $eGFR (mL/min/1.73 m^2) = 175 \times (S_{cr}/88.4)^{-1.154} \times (Age)^{-0.203} \times (0.742$ if female) $\times (1.212$ if African American) (SI units).
 12. Ability to swallow capsules and comply with outpatient treatment, laboratory monitoring, and required clinic visits for the duration of study participation.
 13. Willingness of men and women of reproductive potential to observe conventional and effective birth control for the duration of treatment and for 3 months following the last dose of study treatment; this may include barrier methods such as a condom or diaphragm with spermicidal gel.

Notes:

- A postmenopausal woman will be defined as having no menses for 12 months without an alternative medical cause. Male sterility will be defined as only men sterilized surgically. For male patients with a pregnant partner, a condom should be used for contraception. For male patients with a non-pregnant female partner of child-bearing potential and woman of child-bearing potential one of the following birth control methods with a failure rate of less than 1% per year when used consistently and correctly are recommended:
 - a. Combined estrogen and progesterone containing hormonal contraception associated with inhibition of ovulation given orally, intravaginally, or transdermally
 - b. Progesterone-only hormonal contraception associated with inhibition of ovulation given orally, by injection, or by implant

- c. Intrauterine device (IUD)
 - d. Intrauterine hormone-releasing system (IUS)
 - e. Bilateral tubal occlusion
 - f. Vasectomized partner
 - g. Sexual abstinence
 - Birth control methods unacceptable for this clinical trial are:
 - a. Periodic abstinence (calendar, symptothermal, or post-ovulation methods)
 - b. Withdrawal (coitus interruptus)
 - c. Spermicide only
 - d. Lactational amenorrhea method
 - Male study participants should refrain from sperm donation during study treatment and up to 6 months following the last dose of selpercatinib.
14. Written informed consent and any local required authorization (e.g., Health Insurance Portability and Accountability Act in the US, European Union [EU] Data Privacy Directive in the EU) obtained from the patient/legal representative prior to performing any protocol-related procedures, including screening evaluations.
15. Cohorts 1 and 2: failed or intolerant to standard of care; see [Table 4-1](#) for Examples.

Table 4-1 Standard of Care Therapies for Cohort 1 and 2

| Cohort | Therapy |
|--|---|
| Cohort 1: RET Fusion-Positive Solid Tumor | 
NSCLC: platinum-based chemotherapy (or other chemotherapy if not eligible for platinum) or PD-1/PD-L1 immunotherapy or both
 
Thyroid: sorafenib, patients must also be radioactive iodine-refractory as appropriate
 
Colorectal: fluoropyrimidine-based chemotherapy, with or without anti-VEGF-directed therapy or anti-EGFR-directed therapy as appropriate for the disease
 
Pancreas: fluoropyrimidine-based, gemcitabine-based, or S-1 chemotherapy
 
Breast: anthracycline, taxane, HER2-directed therapy and/or hormonal therapy or other standard therapy appropriate for the disease
 
Other: prior standard therapy for the disease
 |
| Cohort 2: RET -mutant MTC | No approved SOC |

Abbreviations: EGFR-epidermal growth factor receptor; HER2-human epidermal growth factor receptor 2; MTC-medullary thyroid cancer; NSCLC-non-small cell lung cancer; PD-1-programmed cell death protein 1; PD-L1-programmed death-ligand 1; VEGF-vascular endothelial growth factor.

16. Cohorts 1-2: enrollment will be restricted to patients with evidence of a *RET* gene alteration in tumor (i.e., not just blood) as defined in [Synopsis Table 1](#) . However, a positive germline DNA test for a *RET* gene mutation as defined in [Appendix B](#) (Table 11-2) is acceptable in the absence of tumor tissue testing for patients with MTC.
17. Cohorts 1-2: at least one measurable lesion as defined by RECIST v1.1 and not previously irradiated (unless PD for the irradiated lesion[s] has been radiographically documented).
18. Cohort 2: radiographic PD within the previous 14 months for systematic treatment naïve patient.

Note:

Patients otherwise eligible for Cohort 2 who do not demonstrate radiographic PD within the previous 14 months may be enrolled to Cohort 3 if a compelling rationale is provided by the Investigator and approved by the Sponsor.

4.2 Exclusion Criteria

19. Cohorts 1-2, an additional validated oncogenic driver that could cause resistance to selpercatinib treatment if known. See [Appendix C \(Table 11-3\)](#) for examples.
20. Prior treatment with a selective RET inhibitor(s) (including investigational selective RET inhibitor(s), such as BLU-667, RXDX-105, etc.)
21. Are currently enrolled in any other clinical study involving an investigational product or any other type of medical research judged not to be scientifically or medically compatible with this study
22. Investigational agent or anticancer therapy within 5 half-lives or 2 weeks (whichever is shorter) prior to planned start of selpercatinib. In addition, no concurrent investigational anticancer therapy is permitted.

Notes:

- Refer to Section [6.3.2](#) of the main protocol for allowable concurrent therapies.
 - Selpercatinib may be started within less than 5 half-lives or 2 weeks of prior therapy if considered by the Investigator to be safe and within the best interest of the patient, with prior sponsor approval.
23. Major surgery (excluding placement of vascular access or biopsy) within 4 weeks prior to planned start of selpercatinib.
 24. Radiotherapy with a limited field of radiation for palliation within 1 week of the first dose of study treatment, with the exception of patients receiving radiation to more than 30% of the bone marrow or with a wide field of radiation, which must be completed at least 4 weeks prior to the first dose of study treatment.
 25. Any unresolved toxicities from prior therapy greater than CTCAE Grade 1 except where otherwise noted in this eligibility criteria at the time of starting study treatment with the exception of alopecia and Grade 2, prior platinum therapy-related neuropathy.
 26. Symptomatic primary CNS tumor, symptomatic CNS metastases, leptomeningeal carcinomatosis, or untreated spinal cord compression.

Exception: Patients are eligible if neurological symptoms and CNS imaging are stable and steroid dose is stable for 14 days prior to the first dose of selpercatinib and no CNS surgery or radiation has been performed for 28 days, 14 days if stereotactic radiosurgery [SRS].

Note:

- All prior local treatments for CNS disease (e.g. surgery, whole brain radiation [WBRT], SRS), the start and stop dates for each prior local therapy, the specific lesions treated (if SRS and/or surgery), whether the patient developed intracranial progression after the last prior local treatment, and which lesions progressed since completion of the local therapy must be documented.
27. Clinically significant active cardiovascular disease or history of myocardial infarction within 6 months prior to planned start of selpercatinib or prolongation of the QT interval corrected for heart rate using Fridericia's formula (QTcF) > 470 msec. Correction of suspected drug-induced QTcF prolongation may be attempted at the investigator's discretion if clinically safe to do so.
 28. History of Human Immunodeficiency Virus (known HIV 1/2 antibodies positive); patients with unknown HIV status do not need to be tested.
 29. History of active hepatitis B (known positive hepatitis B surface antigen [HbsAg] and quantitative hepatitis B DNA greater than the upper limit of detection of the assay) or C (known positive hepatitis C antibody and quantitative hepatitis C RNA greater than the upper limit of detection of the assay); patients with unknown hepatitis B/hepatitis C status do not need to be tested.
 30. Active uncontrolled systemic bacterial, viral, or fungal infection or serious ongoing intercurrent illness, such as hypertension or diabetes, despite optimal treatment. Screening for chronic conditions is not required.
 31. Clinically significant active malabsorption syndrome or other condition likely to affect gastrointestinal absorption of the study drug.
 32. Uncontrolled symptomatic hyperthyroidism or hypothyroidism.
 33. Uncontrolled symptomatic hypercalcemia or hypocalcemia.
 34. Concurrent use of drugs known to prolong QTc (refer to [Appendix D](#) of the main protocol)
 35. Pregnancy or lactation. Breast-feeding should be interrupted when selpercatinib is started; breast-feeding can be resumed 3 months after discontinuation of selpercatinib.
 36. Active second malignancy other than minor treatment of indolent cancers with prior sponsor approval.

5 Enrollment Procedures

For all patients, a copy of the redacted Molecular Pathology Report, or other report(s) describing tumor *RET* (and/or other) alteration analysis must be submitted to the Sponsor or designee during Screening for review prior to patient enrollment.

Individuals who do not meet the criteria for participation in this study (screen failure) may be re-screened, only after discussion with and permission from the Lilly CRP or designee. Patients may be eligible for re-screening up to 2 times in any of the following circumstances:

- Patients who have become eligible to enroll in the study as the result of a protocol amendment.
- Patients whose status has changed such that the eligibility criterion that caused the patient to screen fail would no longer cause the patient to screen fail again.
- Patients who complete screening and meet all inclusion and exclusion requirements but are unable to be enrolled due to extenuating circumstances (such as severe weather, or child illness).

Each time re-screening is performed, the individual must sign a new informed consent form (ICF) and will be assigned a new identification number. If a target gene positive result was obtained for an individual under their first patient number, this result can be linked to their new number in an effort to preserve patient tissue. If a target gene result was not successfully obtained for an individual under their first patient number, then a new sample for this individual (as well as one repeat if needed) can be submitted to the central lab with the new patient number. Repeating of laboratory tests during the screening period does not constitute re-screening.

This is an open-label study, and all patients who meet all criteria for enrollment will receive selpercatinib treatment. Dispensing and tracking selpercatinib treatment will be accomplished using an interactive Web/voice response system (IxRS).

6 Treatment

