Note: All prior local treatments for CNS disease (e.g. surgery, whole brain radiation [WBRT], SRS), the start and stop dates for each prior local therapy, the specific lesions treated (if SRS and/or surgery), whether the patient developed intracranial progression after the last prior local treatment, and which lesions progressed since completion of the local therapy must be documented.
27. Clinically significant active cardiovascular disease or history of myocardial infarction within 6 months prior to planned start of selpercatinib or prolongation of the QT interval corrected for heart rate using Fridericia's formula (QTcF) > 470 msec. Correction of suspected drug-induced QTcF prolongation may be attempted at the investigator's discretion if clinically safe to do so.
28. History of Human Immunodeficiency Virus (known HIV 1/2 antibodies positive); patients with unknown HIV status do not need to be tested.
29. History of active hepatitis B (known positive hepatitis B surface antigen [HbsAg] and quantitative hepatitis B DNA greater than the upper limit of detection of the assay) or C (known positive hepatitis C antibody and quantitative hepatitis C RNA greater than the upper limit of detection of the assay); patients with unknown hepatitis B/hepatitis C status do not need to be tested.
30. Active uncontrolled systemic bacterial, viral, or fungal infection or serious ongoing intercurrent illness, such as hypertension or diabetes, despite optimal treatment. Screening for chronic conditions is not required.
31. Clinically significant active malabsorption syndrome or other condition likely to affect gastrointestinal absorption of the study drug.
32. Uncontrolled symptomatic hyperthyroidism or hypothyroidism.
33. Uncontrolled symptomatic hypercalcemia or hypocalcemia.
34. Concurrent use of drugs known to prolong QTc (refer to [Appendix D](#) of the main protocol)
35. Pregnancy or lactation. Breast-feeding should be interrupted when selpercatinib is started; breast-feeding can be resumed 3 months after discontinuation of selpercatinib.
36. Active second malignancy other than minor treatment of indolent cancers with prior sponsor approval.

PLANNED SAMPLE SIZE:

The study will enroll approximately 75 patients in total.

INVESTIGATIONAL PRODUCT:

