Treatment may be delayed for a maximum of 28 days to allow a patient sufficient time for recovery from selpercatinib-related toxicity. If a patient does not recover from the toxicity within 28 days from the time of last treatment, the patient must be discontinued from selpercatinib. In rare circumstances, a delay >28 days may be permitted before discontinuing the patient from treatment, as long as the patient demonstrates clinical benefit without objective progression and is recovering from the toxicity. Such circumstances should be discussed between Sponsor and Investigator and documented.

Table 6-1 Suggested Toxicity Management for all Parts of this Study

| Dose Level | Dose of Selpercatinib |
|---------------------------------|---|
| Starting Dose | 160 mg BID |
| First Dose Reduction | 120 mg BID* |
| Second Dose Reduction | 80 mg BID* |
| Third Dose Reduction and Beyond | Only permitted if there is a compelling clinical rationale articulated by the Investigator and approved by the Sponsor. |

Abbreviations: AE-adverse events; BID-twice daily; LFT-liver function test.

*For the specific AEs of hypersensitivity reactions, LFT increases, thrombocytopenia and hypertension, the Sponsor may recommend a lower starting dose (i.e. 40 mg BID for hypersensitivity reactions and 80 mg BID for certain LFT increases, 120 mg BID for thrombocytopenia) upon resumption of study drug treatment, with subsequent dose escalation if tolerated without clinically significant recurrence of the AEs. Occurrence of these AEs should be discussed with the Sponsor.

All dose interruptions and dose modifications and the reasons for those changes will be recorded in the electronic Case Report Form (eCRF).

Guidance for Investigator on Specific Adverse Events

Dose Modifications for Selpercatinib Hypersensitivity

Please refer to the IB for the most current guidance on management of selpercatinib hypersensitivity reactions. Recommended actions are shown below.

If selpercatinib drug hypersensitivity is suspected, study drug should be withheld and treatment with steroids at 1 mg/kg prednisone (or equivalent) should be initiated. Upon resolution, selpercatinib may be resumed at a reduced dose of 40 mg BID while continuing steroids at the same dose. Note that this dose reduction does not require sponsor approval. Hypersensitivity has recurred in some patients, typically at 3 to 6 hours following drug administration. Follow the guidelines below if hypersensitivity recurs:

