Appendix K Protocol Amendment History

The Protocol Amendment Summary of Changes Table for the current amendment is located directly before the Table of Contents (TOC).

Protocol Amendment Summary of Changes Table

| DOCUMENT HISTORY | |
|----------------------|-------------|
| Document | Date |
| Protocol J2G-GH-JZJK | 30-Jul-2019 |

Amendment [a]: (20 July 2020)

This amendment is considered to be substantial based on the criteria set forth in Article 10(a) of Directive 2001/20/EC of the European Parliament and the Council of the European Union.

Overall Rationale for the Amendment:

| Section # and Name | Description of Change | Brief Rationale |
|---|---|--------------------------------------|
| Synopsis, and 3.4 Investigational Plan | Enrollment in Cohort 1 was clarified as “For lung cancer, only patients harboring RET-KIF5B , RET-CCDC6 , RET-NCOA4 can be enrolled in Cohort 1. For other solid tumor, patients with any RET fusion can be enrolled in Cohort 1”. Added inclusion criteria to Cohort 3 as “Other RET -altered solid tumor or other RET alteration/activation not meeting the requirements for Cohorts 1 or 2”. | Clarification |
| Synopsis, and 4.1 Inclusion Criteria | Add additional information to clarify calculation of eGFR. | Clarification |
| Synopsis, and 4.2 Exclusion Criteria | Metastases was clarified as symptomatic CNS metastases in exclusion criterion 26. “Lower limit of detection of the assay” was updated to “upper limit of detection of the assay” in Exclusion Criterion 29; removed exclusion criterion 34 and 35. | Clarification |
| 1.1 Tumors with RET Abnormalities and Current Treatment Options, 1.4 Determination Starting Dose | Updated related contents per latest IB. | To be consistent with IB version 7.0 |
| 1.5 Clinical Experience | Updated new data of LIBRETTO-001 study. | To be consistent with IB version 7.0 |
| 1.6.1 Known and Anticipated Risks | Replaced risks based on animal studies with risks based on clinical studies. | To be consistent with IB version 7.0 |

| Section # and Name | Description of Change | Brief Rationale |
|---|---|--|
| 1.6.2 Potential Drug Interactions, 6.3.3 Other Concomitant Medications, Appendix D and Appendix E | Updated drug interaction part and concomitant medication guidance per latest IB. | To be consistent with IB version 7.0 |

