6.11.2.2. Adverse Events of Special Interest

Based upon information available to date and/or known class effects of this compound, several categories of AE have been designated to be of special interest. These include the following which are discussed below:

- Hepatic effects/potential liver toxicity (elevated levels of ALT, AST, total bilirubin, direct bilirubin, and ALP)
- Hypersensitivity
- Hypertension
- Thrombocytopenia

Liver function tests will be presented using conventional summary statistics, toxicity shift table analysis, and by time-to-event plots. Possible drug-induced liver injury will be assessed as defined in FDA guidance. Hy's Law cases of drug-induced liver injury have the following components:

- The drug causes hepatocellular injury as evidenced by an elevation of ALT or AST to 3-fold or greater of the upper limit of normal (ULN) relative to control (or in this context to baseline levels)

- In addition to the transaminase increases, an associated (i.e. concomitant) elevation of total serum bilirubin to 2-fold or greater of the ULN without initial findings of cholestasis (elevated alkaline phosphatase)
- No other explanation can be found for the combination of increased transaminase(s) and total bilirubin such as viral hepatitis, pre-existing acute liver disease, or concomitant drug capable of causing the observed injury

Events of hypersensitivity will be identified using search terms that include the preferred terms *Hypersensitivity* and *Drug hypersensitivity* under the *Immune System Disorders* MedDRA system organ class.

Events of hypertension will be identified using the preferred terms *Blood pressure abnormal* and *Blood pressure increased* under the *Investigations* system organ class, as well as the preferred term *Hypertension* under the *Vascular Disorders* system organ class.

Events of thrombocytopenia will be identified using the preferred term *Thrombocytopenia* under the *Blood and lymphatic system disorders* system organ class, as well as the preferred term *Platelet count decreased* under the *Investigations* system organ class.

Additional AEs of special interest may be added based on review of the safety data before the final data extraction.

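### Exclusion criterion 29 sets its hepatitis B and C viral-load limit at the top of the assay's range, so it passes any in-range viral load and does not identify the active hepatitis it names

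*Protocol*

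**What the plan says.** Criterion 29 appears with the same limits in the Protocol synopsis and in Section 4.2. Its stated target is "History of active hepatitis B", or hepatitis C. Each arm has two conditions that must both be met:

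- Hepatitis B: known positive surface antigen, and "quantitative hepatitis B DNA greater than the upper limit of detection of the assay".
- Hepatitis C: "known positive hepatitis C antibody and quantitative hepatitis C RNA greater than the upper limit of detection of the assay".

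The criterion closes by saying that "patients with unknown hepatitis B/hepatitis C status do not need to be tested".

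The wording is current and was chosen by an explicit edit. Appendix K, under the amendment of 20 July 2020, records that the lower limit "was updated to “upper limit of detection of the assay” in Exclusion Criterion 29" and gives the rationale as a clarification.

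On the analysis side, SAP Section 6.11.2.2 lists hepatic effects among the adverse events of special interest. It makes the following a component of a Hy's Law case: "No other explanation can be found for the combination of increased transaminase(s) and total bilirubin such as viral hepatitis".

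**The concern.** An eligibility rule for active viral hepatitis should separate patients with a meaningful viral load from those without one. This rule puts the dividing line at the ceiling of the assay. A site that applies it as written would let through a known carrier with any viral load the assay can report as a number.

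Two things are at stake:

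- **Safety.** The drug has a documented liver signal. Protocol Section 1.5 reports, for the prior study, increased ALT in 31.5% of patients (Grade 3-4 in 9.8%) and increased AST in 31.9% (Grade 3-4 in 7.8%).
- **Interpretation.** A liver event in a patient who entered with known viremia has a competing explanation from the outset, and the SAP's Hy's Law definition turns on whether such an explanation exists.

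**Working it through.** The plan states no figure to reproduce. The check sets the texts side by side.

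**Step 1: apply criterion 29 literally.** Let U be the assay's upper limit of detection and V the patient's viral load. The rule excludes only if serology is known positive and V > U.

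- Known positive, virus not detected: V is below U, so not excluded.
- Known positive, V reported as a number within range: V ≤ U, so V > U is false and the patient is not excluded, however high V is.
- Known positive, result off the top of the scale: V > U, so excluded.
- Status unknown: no test is required, so not excluded.

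The second line contradicts the word 'active'. The same logic holds for hepatitis B DNA and hepatitis C RNA, and in both places where the criterion stands.

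**Step 2: look for another criterion that does the job.**

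- Inclusion 10 (Section 4.1) limits ALT or AST to 2.5 times ULN (5 times with liver involvement) and total bilirubin to 1.5 times ULN (3 times with liver involvement). A viremic patient inside those limits passes.
- Exclusion 30 (Section 4.2) covers active uncontrolled systemic infection, viral infection included. It works by judgement, names neither hepatitis nor a viral load, and says chronic conditions need not be screened for.
- Table 7-1 and Appendix H list no hepatitis serology or viral-load test.

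Both criteria could stop some of these patients. Neither sets a viral-load limit.

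**Step 3: try to size it.** Let f be the share of known viremic patients whose viral load is above U. The share that passes criterion 29 is 1 − f, before inclusion 10 and exclusion 30 act. The documents do not give f. Purely as an assumption, f = 1% gives 1 − 0.01 = 99% and f = 20% gives 1 − 0.20 = 80%. To turn either into a number of patients would also need the prevalence of known carriers among those screened, which is not given.

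**Step 4: who enrolled under this wording.** The amendment is dated 20 July 2020, and Section 10.1 requires ethics approval before a change is implemented. SAP Section 6.14 expected an interim cutoff of 31 July 2020, chosen so that about half of enrolled patients had a post-baseline tumor assessment. The earliest scheduled scan is the optional one at week 4 (±7 days), that is 28 − 7 = 21 days after first dose. A patient with a scheduled scan by 31 July therefore started by about 31 − 21 = 10 July, before the amendment. If that cutoff held, a substantial group entered under the preceding wording. Whether this is half of 75 or half of those enrolled by then is not clear from the text.

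**The case against.** Several points on the other side are fair.

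- **Passing criterion 29 is not the same as being eligible.** A reader might infer that almost every patient with active viremia can enter. The documents do not support that. It would need the assay ceiling and the viral-load distribution, and it ignores inclusion 10 and exclusion 30. An investigator could use exclusion 30 to keep out a patient with a very high load.
- **The liver-event counts do not measure the defect.** Applying the prior-study rates to 75 patients gives 75 × 0.315 = 23.6 ALT increases and 75 × 0.098 = 7.4 at Grade 3-4. These are totals for all patients whatever their hepatitis status, and correcting criterion 29 would leave them essentially unchanged.
- **Liver events would not become unattributable.** The patients concerned are known positives, so the competing cause is visible. Section 6.2.4 calls for a work-up of other causes, viral serologies included, at Grade 3 or higher liver tests. Section 8.2.2.1 adds repeat testing and follow-up against baseline. Attribution is harder, not impossible.
- **Steroids.** A reader might connect this point with the hypersensitivity rule that "treatment with steroids at 1 mg/kg prednisone (or equivalent) should be initiated". Nothing in the documents links steroid treatment to viral hepatitis, so the point does not rest on it.
- **Reach of a correction.** Patients of unknown status would still not be tested.
- **Intended meaning.** The change to the upper limit was explicit, and the sponsor may have meant something like a laboratory reference limit. The text does not say so. With about 40 sites planned, a literal reading and a guessed one would admit different patients.

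These points limit the size of the problem. They leave standing that an in-range result cannot meet the exclusion as written.

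**Conclusion.** Criterion 29 is wrong as written. Followed literally, it excludes only known positive patients whose viral load is off the top of the assay, so it fails to identify active hepatitis B or C. It is an operative safety rule that gives the wrong answer when applied, and the two neighbouring criteria cover the gap only in part.

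The number of patients affected is unknown and may be small, and some may have entered before the wording took effect. The consequence supported by the documents is harder attribution of liver events in known viremic patients, in a trial where hepatic effects are of special interest. No effect on the primary endpoint, IRC-assessed ORR, is shown. The conclusion assumes only that the upper limit of detection carries its plain meaning, the highest value the assay can report.

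**What to change.** In the synopsis and in Section 4.2, reconcile the threshold phrase with the word 'active' for both hepatitis B DNA and hepatitis C RNA. The criterion should state a limit that an in-range quantitative result can exceed. The sponsor sets the value, and all sites apply the same one. If a different meaning was intended in the July 2020 edit, the text should state it.

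For patients already enrolled, identify those known to be HBsAg-positive or hepatitis C antibody-positive, and flag them in the hepatic and Hy's Law review.

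The cost is one phrase in two places at the next amendment. No new test is needed, because the criterion already relies on a quantitative result in known positives. The downside is that a few known viremic carriers may no longer qualify.
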